1.3 EXPECTED SAMPLE SIZE

Approximately 213 participants with PV or PF will be randomized as follows for 1904 study:

- Approximately 183 participants with PV will be randomized in a 2:1 ratio to receive efgartigimod PH20 SC or placebo, respectively
- Up to approximately 30 participants with PF may be randomized in a 2:1 ratio to receive efgartigimod PH20 SC or placebo, respectively

All participants who were randomized into ARGX-113-1904 will be eligible to roll over to study 1905.

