4.1.3 Presentation of results and statistical analysis

Wherever the stratification factors will be used in the efficacy analyses, the eCRF values of these will be used and not the ones coming from the randomization. Also for participants randomized without disease status, disease severity and body weight stratification, i.e. Japanese and PF participants, these factors will be derived from the eCRF in order to include these participants in the statistical models.

For the analysis of the PF only population, all stratified models/tests for binary and survival endpoints will only be stratified by the following 2 strata: relapsing vs. newly-diagnosed.

Examples of SAS code for the statistical analysis procedures are provided in Appendix 9.1.5.

	Statistical Analysis Plan	
ARGX-113-1904	Final analysis	Final 2.0 of 22NOV2023

Frequency tabulations will be provided of the percentage of PV participants having achieved CRmin within 30 weeks (primary endpoint). The table will be repeated for subgroups including treatment differences in proportions with 95% Wald CI, and overall (PV+PF participants).

A stratified CMH test will be calculated with the stratification factors of disease status, disease severity, and body weight at randomization; the strata-adjusted difference in proportions with the Klingenberg midpoint and 95% confidence interval and 2-sided CMH test p-value will be provided as well as an adjusted common OR with its 95% confidence interval. Homogeneity of the odds ratios will be tested by means of a Breslow Day test with Tarone's adjustment.

A supplementary analysis using the treatment policy strategy will be done for PV participants and overall.

The supplementary landmark analysis at week 30 will be performed on the mITT population for PV participants and overall using the stratified CMH test.

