4.1.5 Subgroup analyses for efficacy

Subgroups are defined based on the following categorizing factors:

- Gender (Male, Female)
- Age (18 -< 65, 65 -<75, >=75 years)
- Weight at screening (<50, 50-<75, 75 -< 100, 100 -<125, >= 125 kg)
- BMI at screening (Underweight: < 18.5 kg/m², Normal weight: 18.5 -< 25 kg/m², Overweight: 25 -< 30 kg/m², Obese: >= 30 kg/m²)
- Race (Asian, Black or African American, White, Other)
- Baseline eGFR (Normal: >= 90 mL/min/1.73m², Mildly impaired: 60 -<90 mL/min/1.73m², Moderately impaired: 30 -< 60 mL/min/1.73m², Severely impaired: <30 mL/min/1.73m²)
- Disease type (PV/PF) and PV subtype (mucosal-dominant vs (muco-)cutaneous)
- Disease status (relapsing vs newly diagnosed)
- Disease severity (PDAI activity score <30 and PDAI activity score ≥30); moderate (15≤PDAI ≤44) vs severe (PDAI ≥45)
- Region (North America; Europe; Asia; Rest of World)

Subgroup analyses will be performed on the primary and key secondary efficacy endpoints on the mITT population.

Following table summarizes the analyses:

Table 5: Summary of analyses

Endpoint	PV	PF ^f	All (PV+PF)	Strategy
Proportion CRmin	X ^{1,c,p}	X	X ^{2,c,p,s}	C+T
NCPD	X ^{2,c,p}	X	X ^{2,s}	H+T
Time to CR	X ^{2,c,p}	X	X ^{2,s}	C+T
Time to DC	X ^{2, c,p}	X	X ^{2,s}	C+T
Time to CRmin	X	X	X	C
Proportion DC / CR	X	X	X	C
Proportion treatment failure	X		X	T
Number of flares (incidence rate)	X		X	T
Proportion of participants with flare	X		X	T
Time to first flare	X		X	T
Duration of CRmin	X	X	X	T
PDAI, QoL, C-GTI	X		X	T
¹ Primary endpoint ² Key secondary endpoint ^c Besides main analysis also supplementary analysis will be performed. ^f PF as part of subgroup analysis or as separate analysis. ^p Also analysis on PP analysis set and mITT excluding data impacted by the conflict in Ukraine will be performed. ^s Also subgroup analyses will be performed. C=composite strategy (taking into account ICEs) H=hypothetical strategy (taking into account ICEs) T=treatment policy strategy (ignoring ICEs)				

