6. CHANGES TO THE PLANNED ANALYSIS

6.1 CHANGES NOT COVERED BY PROTOCOL AMENDMENTS BEFORE DATABASE LOCK

Analysis visit labels deviate from the visit labels in the schedule of assessments of the protocol to accommodate the example in the ICH E3 guideline annex III.

NCPD, time to CR and time to DC for PV+PF participants are added to the fixed-sequence testing procedure.

NCPD (mg/kg/day) is calculated for different periods as [the sum of (equivalent doses taking into account daily dose frequency)/(body weight in kg)]/(period duration in days) with body weight of visit closest before or at each start of prednisone equivalent medication record instead of using weight at baseline.

The following extra analyses will be conducted, which are not covered in the clinical study protocol (CSP):

- Cox proportional hazard model on time to event endpoints
- Stratified Mann-Whitney test on NCPD and GTI endpoints
- Selected endpoints on the subset of PF participants

The following extra endpoints will be derived, which are not covered in the CSP (see section 4.1.2.3 and 3.5.2):

- Time to CRmin
- NCPD defined for different periods
- Cumulative prednisone dose (mg) over different periods
- Time to first flare for different periods
- Proportions of participants with DC/CR
- Duration of CRmin

The CSP pre-specified a list of medications whose use is to be considered an intercurrent event to be handled using the composite strategy. These medications were: immunosuppressants or dapsone, IVIg at immunomodulating doses, immunoadsorption or plasma exchange, rituximab or anti-CD20 biologics and IV corticosteroids. In this SAP, the following therapies, not mentioned in the CSP, have also been added as intercurrent events to be handled with the composite strategy: tetracyclines and any interventional study drug under development for pemphigus.

The following analysis, covered in the CSP, will not be performed since no comparable historical data are available for the control arm in the PF literature:

- The magnitude of the effect of efgartigimod PH20 SC compared to placebo in the PF subpopulation will be evaluated using the posterior distribution of the treatment effect (difference between efgartigimod PH20 SC and placebo) obtained in a Bayesian analysis. This Bayesian analysis will incorporate historical data for the placebo in an informative maximum a posteriori probability estimate prior with robustness modifier.

	Statistical Analysis Plan	

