14.2.1.2.1.2	Proportion of PV+PF Participants Who Achieved CRmin - Cochran-Mantel-Haenszel (Supplementary Analysis: Treatment Policy) - mITT	mITT	
14.2.1.2.1.3	Proportion of PV+PF Participants Who Achieved CRmin - Cochran-Mantel-Haenszel - PP	PP	
14.2.1.2.1.4	Proportion of PV+PF Participants Who Achieved CRmin - Cochran-Mantel-Haenszel - mITT Excluding Data Impacted by the Conflict in Ukraine	mITT	
14.2.1.2.1.5	Proportion of PV+PF Participants Who Achieved CRmin at 30 Weeks Landmark - Cochran-Mantel-Haenszel - mITT	mITT	TL
14.2.1.2.1.6	Proportion of PV+PF Participants Who Achieved CRmin at 30 Weeks Landmark (Sensitivity Analysis) - Cochran-Mantel-Haenszel - mITT	mITT	
14.2.1.2.1.7	Proportion of PF Participants Who Achieved CRmin - Cochran-Mantel-Haenszel - mITT-PF	mITT	TL
14.2.1.2.1.8	Proportion of PF Participants Who Achieved CRmin at 30 Weeks Landmark - Cochran-Mantel-Haenszel - mITT-PF	mITT	TL
14.2.1.2.2.1	NCPD in PV Participants: Descriptive Statistics - mITT-PV	mITT	TL
14.2.1.2.2.2	NCPD over Planned Treatment Phase in PV Participants: ANCOVA - mITT-PV	mITT	TL
14.2.1.2.2.3	NCPD in PV Participants: Descriptive Statistics - (Supplementary Analysis: Treatment Policy) - mITT-PV	mITT	

	Statistical Analysis Plan	
ARGX-113-1904	Final analysis	Final 2.0 of 22NOV2023

14.2.1.2.2.4	NCPD over Planned Treatment Phase in PV Participants: ANCOVA (Supplementary Analysis: Treatment Policy) - mITT-PV	mITT	
14.2.1.2.2.5	NCPD in PV Participants: Descriptive Statistics - PP-PV	PP	
14.2.1.2.2.6	NCPD over Planned Treatment Phase in PV Participants: ANCOVA - PP-PV	PP	
14.2.1.2.2.7	NCPD in PV Participants: Descriptive Statistics - mITT Excluding Data Impacted by the Conflict in Ukraine-PV	mITT	
14.2.1.2.2.8	NCPD over Planned Treatment Phase in PV Participants: ANCOVA - mITT Excluding Data Impacted by the Conflict in Ukraine-PV	mITT	
14.2.1.2.2.9	NCPD over Planned Treatment Phase in PV Participants: Stratified Mann-Whitney test - mITT-PV	mITT	
14.2.1.2.2.10	NCPD in PF Participants: Descriptive Statistics – mITT-PF	mITT	TL
14.2.1.2.2.11	NCPD over Planned Treatment Phase in PF Participants: ANCOVA – mITT-PF	mITT	TL
14.2.1.2.2.12	NCPD in PV+PF Participants: Descriptive Statistics - mITT	mITT	TL
14.2.1.2.2.13	NCPD over Planned Treatment Phase in PV+PF Participants: ANCOVA - mITT	mITT	TL
14.2.1.2.2.14	Cumulative Prednisone dose in PV Participants: Descriptive Statistics - mITT-PV	mITT	

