14.2.1.2.2.15	Cumulative Prednisone dose in PV+PF Participants: Descriptive Statistics - mITT	mITT	
14.2.1.2.3.1	Time to DC in PV Participants: Descriptive Statistics - Logrank Test - mITT-PV	mITT	TL
14.2.1.2.3.2	Time to DC in PV Participants: Cox Regression - mITT-PV	mITT	TL
14.2.1.2.3.3	Time to DC in PV Participants: Descriptive Statistics (Supplementary Analysis: Treatment Policy) - Logrank Test - mITT-PV	mITT	
14.2.1.2.3.4	Time to DC in PV Participants (Supplementary Analysis: Treatment Policy): Cox Regression - mITT-PV	mITT	
14.2.1.2.3.5	Time to DC in PV Participants: Descriptive Statistics - Logrank Test - PP-PV	PP	
14.2.1.2.3.6	Time to DC in PV Participants: Descriptive Statistics - Logrank Test - mITT Excluding Data Impacted by the Conflict in Ukraine-PV	mITT	

	Statistical Analysis Plan	
ARGX-113-1904	Final analysis	Final 2.0 of 22NOV2023

14.2.1.2.3.7	Time to DC in PF Participants: Descriptive Statistics - Logrank Test – mITT-PF	mITT	TL
14.2.1.2.3.8	Time to DC in PV+PF Participants: Descriptive Statistics - Logrank Test - mITT	mITT	TL
14.2.1.2.3.9	Time to DC in PV+PF Participants: Cox Regression - mITT	mITT	TL
14.2.1.2.4.1	Time to CR in PV Participants: Descriptive Statistics - Logrank Test - mITT-PV	mITT	TL
14.2.1.2.4.2	Time to CR in PV Participants: Cox Regression - mITT-PV	mITT	TL
14.2.1.2.4.3	Time to CR in PV Participants: Descriptive Statistics (Supplementary Analysis: Treatment Policy) - Logrank Test - mITT-PV	mITT	
14.2.1.2.4.4	Time to CR in PV Participants (Supplementary Analysis: Treatment Policy): Cox Regression - mITT-PV	mITT	
14.2.1.2.4.5	Time to CR in PV Participants: Descriptive Statistics - Logrank Test - PP-PV	PP	
14.2.1.2.4.6	Time to CR in PV Participants: Descriptive Statistics - Logrank Test - mITT Excluding Data Impacted by the Conflict in Ukraine-PV	mITT	
14.2.1.2.4.7	Time to CR in PF Participants: Descriptive Statistics - Logrank Test - mITT-PF	mITT	TL
14.2.1.2.4.8	Time to CR in PV+PF Participants: Descriptive Statistics - Logrank Test - mITT	mITT	TL
14.2.1.2.4.9	Time to CR in PV+PF Participants: Cox Regression - mITT	mITT	TL
14.2.1.2.5.1	Proportion of Participants Who Achieved CRmin - by Subgroups	mITT	TL
14.2.1.2.5.2	Proportion of PV Participants Who Achieved CRmin – mITT-PV - by Subgroups	mITT	TL
14.2.1.2.5.3	NCPD: Descriptive Statistics - mITT - by Subgroups	mITT	
14.2.1.2.5.4	Time to DC: Descriptive Statistics - mITT - by Subgroups	mITT	
14.2.1.2.5.5	Time to CR: Descriptive Statistics - mITT - by Subgroups	mITT	

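### Subgroup CRmin differences carry a plain 95% Wald interval, which covers about 91–93% at the PF ceiling of 20:10 if PV planning rates hold there

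*SAP*

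**What the plan says.** SAP 4.1.3 first describes frequency tables for CRmin within 30 weeks and then says: "The table will be repeated for subgroups including treatment differences in proportions with 95% Wald CI". The strata-adjusted difference, with a Klingenberg midpoint and interval and a stratified CMH p-value, is described separately. The subgroup interval is therefore read here as the unadjusted two-sample Wald interval. No continuity correction is mentioned.

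The factors in SAP 4.1.5 include "Disease type (PV/PF) and PV subtype (mucosal-dominant vs (muco-)cutaneous") and "Weight at screening (<50, 50-<75, 75 -< 100, 100 -<125, >= 125 kg"). SAP 1.3 sets the PF ceiling: "Up to approximately 30 participants with PF may be randomized in a 2:1 ratio".

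SAP 8.1 lists two subgroup tables for this endpoint, both marked for topline:

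- 14.2.1.2.5.1, "Proportion of Participants Who Achieved CRmin - by Subgroups", in which PF is a level.
- 14.2.1.2.5.2, the PV-only counterpart ("mITT-PV - by Subgroups").

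PF also has its own topline table, 14.2.1.2.1.7: "Proportion of PF Participants Who Achieved CRmin - Cochran-Mantel-Haenszel - mITT-PF". SAP 6.1 drops the planned Bayesian PF analysis because "no comparable historical data are available for the control arm in the PF literature".

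**The concern.** The Wald interval estimates each arm's variance from its observed proportion. With about 10 placebo participants and a low response rate, zero placebo responders is a common outcome. The formula then assigns that arm no variance at all, and the interval comes out too short and shifted in favour of the drug.

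The SAP thus uses its weakest interval where groups are smallest. The main analysis uses a Klingenberg interval, and SAP 4.4.3 asks for an exact interval when CRmin is compared across antibody categories. With the Bayesian PF analysis gone, readers of the topline results will rely on simple PF displays such as this one. At stake is whether an interval labelled 95% has close to 95% coverage. No confirmatory conclusion depends on it.

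**Working it through.** **Inputs.** PF at most about 30 at 2:1 gives 20:10 (SAP 1.3). Protocol 9.3 gives rates for PV only: 50% vs 20% (primary assumption), 40% vs 10% (one cell of Table 6) and 34% vs 11% (the additional off-IMP analysis, a different endpoint). Table 6 spans 40–50% vs 1–20%, 15 pairs. Applying any of these to PF is an assumption.

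**The plan's own figures.** The documents state no coverage beyond the nominal 95%. Their power statements reproduce from these rates: 84:42 at 50/20 gives 92.5% (pooled z) or 90.6% (Fisher) against the stated more than 90%; 122:61 at 34/11 gives 94.7% against 95%.

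**Formulas.** With d = p̂₁ − p̂₂:

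- Wald: d ± 1.96·√[p̂₁(1−p̂₁)/n₁ + p̂₂(1−p̂₂)/n₂], no continuity correction.
- Newcombe, from the Wilson limits (l, u) of each arm: lower d − √[(p̂₁−l₁)² + (u₂−p̂₂)²]; upper d + √[(u₁−p̂₁)² + (p̂₂−l₂)²].

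Coverage is the sum of binomial probabilities over all 21 × 11 outcomes whose interval contains the true difference.

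**Results at 20:10**

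| True rates | Wald coverage | Lower limit above truth | Upper limit below truth | Newcombe coverage | Lower limit above truth | Upper limit below truth |
|---|---|---|---|---|---|---|
| 34/11 | 91.3% | 6.7% | 2.0% | 95.9% | 0.5% | 3.6% |
| 40/10 | 93.1% | 4.7% | 2.1% | 96.1% | 0.2% | 3.6% |
| 50/20 | 91.9% | 6.0% | 2.1% | 95.1% | 0.8% | 4.1% |

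Over the 15 Table 6 pairs, Wald runs from 89.2% (45/1) to 94.4% (40/5) and Newcombe from 94.7% (40/20) to 97.2% (40/1). Wald misses favour the drug in 13 of the 15. The exceptions are 40/1 (1.9% above, 5.1% below) and 45/1 (5.3% above, 5.6% below).

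**Mechanism.** P(0 of 10 placebo responders) is 0.9¹⁰ = 0.349 at a 10% rate and 0.8¹⁰ = 0.107 at 20%. Most Wald misses at the three pairs come from these outcomes. Take 8/20 vs 0/10:

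- Wald: 0.400 ± 1.96·√(0.4·0.6/20 + 0) = 0.400 ± 0.215, or 0.185 to 0.615.
- Newcombe: the Wilson limits are 0.219–0.613 and 0–0.278, so the lower limit is 0.400 − √(0.181² + 0.278²) = 0.069 and the upper is 0.613.

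**No true effect, 20:10.** The Wald interval lies wholly above zero 7.2% of the time at 20% in both arms, 4.7% at 10% and 1.0% at 5%. Newcombe gives 1.0%, 0.1% and 0.0%.

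**Other sizes (same three pairs).**

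- Smallest PV weight band: 183/5 = 36.6, so it holds at most 36, or 24:12 if 2:1 holds. Wald covers 93.2–94.6% and Newcombe 94.4–95.3%.
- 12:6 (assumed; not in the documents): Wald 87.1–94.3%, Newcombe 94.9–96.1%.
- 40:20 and 60:30 (assumed): Wald 93.7–94.6%.
- Full PV size, 122:61: Wald about 94.6%. The shortfall is a small-group effect.

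**The case against.** **Continuity correction.** The SAP does not rule one out and its SAS code is redacted. With the usual correction, coverage at 20:10 is 95.9–98.1% at the three pairs and the shortfall disappears. But a plain Wald interval with no correction mentioned means the uncorrected form, and if a correction was intended the SAP needs to say so.

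**Borrowed rates.** There are no PF rates, and 34/11 was set for a different endpoint. That is correct, so the 91–93% figure is conditional. Coverage nevertheless stays below 95% at every Table 6 pair.

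**Erratic deficit.** At 12:6 with 34/11, Wald covers 94.3%, better than at 20:10. With 5% in both arms at 20:10 it covers 98.6%. This stands: the shortfall cannot be claimed for every small level and every rate. The weight-band ceiling is likewise only a bound, and the loss there is 0.4–1.8 points.

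**Choice of replacement.** Newcombe's misses lean the other way, and alternatives such as Agresti–Caffo (96.1–96.4% at 34/11 and 50/20) also restore coverage. This is fair, but it argues about which interval should replace Wald and does not support keeping Wald.

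**No decision depends on it.** Also true. The fixed sequence in SAP 4.1.4 contains no subgroup interval, and PF has its own CMH table. That sets the severity at minor.

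**Conclusion.** The concern holds, as a minor correction. At the PF ceiling of 20:10, the interval labelled 95% covers about 91–93% at the three planning pairs and 89–94% over Table 6, usually erring in the drug's favour. This rests on three assumptions: PV planning rates apply to PF, allocation is exactly 20:10, and the Wald interval is uncorrected. At subgroup sizes of 40:20 and above the loss is about 1 point or less. Only the descriptive intervals in the two subgroup CRmin tables are affected.

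**What to change.** In SAP 4.1.3, replace the Wald interval for subgroup differences in CRmin proportions with the Newcombe score interval, named explicitly, and apply it in Tables 14.2.1.2.5.1 and 14.2.1.2.5.2. The cost is one SAP sentence and one standard procedure option, with no change to endpoints, alpha or data collection.

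The downside is a conservative lower limit in small levels. At 20:10 and 40% vs 10%, the chance that it exceeds zero falls from 59% to 37%. Newcombe's upper limit falls below the true difference 3.6–4.1% of the time at the three pairs, against a nominal 2.5%.

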1.2 STUDY DESIGN

This study is a prospective, multicenter, randomized, double-blinded, placebo-controlled study to investigate the efficacy, safety, participant outcome measures, tolerability, immunogenicity, PK, and PD of efgartigimod PH20 SC in adult participants with PV or PF.

The study comprises a screening period of up to 3 weeks, a treatment period of up to 30 weeks, and an 8-week follow-up period for participants who do not enrol into the open-label extension (OLE) study ARGX-113-1905.

After confirmation of eligibility, participants will be randomized in a 2:1 ratio to receive efgartigimod PH20 SC or placebo, as follows:

- Efgartigimod PH20 SC will be administered on day 1 and day 8 at a dose of [REDACTED] mg, followed by weekly administrations of 1000 mg until CRmin is observed. Efgartigimod PH20 SC will be administered at on-site visits until CR, with a minimum of 6 weekly on-site visits. After achieving CR, efgartigimod PH20 SC will be administered at on-site visits or at home by a nurse until CR on minimal therapy is achieved.
- Placebo (vehicle with 2000 U/mL of rHuPH20) SC will be administered using the same regimen.

CR is defined as the absence of new lesions and complete healing of established lesions (except for post-inflammatory hyperpigmentation or erythema from resolving lesions). CRmin is defined as the absence of new lesions and complete healing of established lesions while the participant is receiving minimal prednisone therapy of ≤ 10 mg/day for at least 2 months (8 weeks).

Randomization will be stratified by disease status (relapsing and newly diagnosed), disease severity (PDAI activity score < 30 and PDAI activity score ≥ 30), and body weight (< 77.5 kg and ≥ 77.5 kg) at baseline. Participants with severe PV or PF (PDAI activity score ≥ 45) will comprise a maximum of 30% of the overall study population.

All participants, regardless of treatment assignment, will concomitantly receive oral prednisone (or equivalent such as prednisolone) at 0.5 mg/kg qd starting dose. Except for oral prednisone (or equivalent), no other systemic therapies (eg, immunosuppressants, IVIg, immunoadsorption, anti-CD20 biologics) will be permitted during the study.

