- Intercurrent medications (see section 3.4.2) before CR: participant is assumed to not reach CR until the theoretical end of the study and is censored at day 218.
- Discontinuation of IMP before CR due to lack of efficacy: participant is assumed to not reach CR until the theoretical end of the study and is censored at day 218.

Participants without any disease assessment are censored at day 1. Participants with disease assessment but not achieving CR in the period from Day 1 to Day 218 and without intercurrent event in that period are censored at the earliest of day 218 and the end of treatment + FU phase.

A supplementary analysis for this secondary endpoint will use the ‘treatment policy strategy’ where the occurrence of the intercurrent event is considered irrelevant: Time to CR is calculated regardless of whether or not the intercurrent event occurs.

4) Time to DC in PV participants, calculated as the difference between the first date DC was achieved and the first IMP administration date. Similar calculations, ICE handling and censoring rules are applied as for ‘time to CR’ (composite strategy).

A supplementary analysis for this secondary endpoint will use the ‘treatment policy strategy’ where the occurrence of the intercurrent event is considered irrelevant: time to DC is calculated regardless of whether or not the intercurrent event occurs.

Both time to event endpoints will be statistically evaluated using the stratified Fleming-Harrington weighted logrank statistic FH (1,0), with the stratification factors disease status, disease severity, and body weight at randomization. For both, Kaplan-Meier survival plots by treatment arm will be produced (as in-text figures only).

5) NCPD over the whole planned treatment phase in all participants: same derivation as second key secondary endpoint (composite strategy and treatment policy strategy) but for all participants.

6) Time to DC in all participants: same derivation as fourth key secondary endpoint (composite strategy) but for all participants.

7) Time to CR in all participants: same derivation as third key secondary endpoint (composite strategy) but for all participants.

	
Statistical Analysis Plan
	

ARGX-113-1904
	
Final analysis
	
Final 2.0 of 22NOV2023

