4.1.2.3 OTHER SECONDARY ENDPOINTS (NOT ALPHA CONTROLLED)

All other secondary endpoints will be analyzed using the mITT population. Analyses related to data in the period after an event (CRmin, DC) can only be performed in participants with that event.

1. Proportion of PF participants who achieve CRmin within 30 weeks: same derivation as for the primary endpoint (composite strategy) but then for PF participants.
2. Time to CRmin in PV, PF and all participants: same derivation as third key secondary endpoint (composite strategy) but using date of achieving CRmin. Time to CRmin is defined as the time to the moment that the participant achieves CRmin status defined as complete remission while receiving prednisone therapy at 10 mg/day or less for at least 8 weeks, based on the assessment of the investigator. The 8-week period with minimal prednisone necessary to confirm CRmin is included as part of this time period. For example, a participant that achieves complete remission with prednisone ≤ 10 mg/day at week 15 for the first time and maintains this status for 8 weeks will have a time to CRmin of $15 + 8 = 23$ weeks.
3. Proportion of participants achieving DC in PV, PF and all participants (composite strategy)
4. Proportion of participants achieving CR in PV, PF and all participants (composite strategy)

For all subsequent secondary endpoints a treatment policy strategy is applied ignoring ICEs.

5. Proportion of treatment failures as assessed by the investigator in PV and in all participants. Specific reasons for treatment failure can be derived as follows in following order:
 - absence of DC: if participant didn't achieve DC as assessed by the investigator
 - prednisone related SAE: occurrence of an SAE after DC considered related to prednisone by the investigator
 - flare: if previous 2 reasons are not applicable, the reason must be a flare between DC and CRmin that is not controlled by a prednisone dose that is 2 dose levels above the dose at which the flare is observed and that is a least 0.3mg/kg qd

Failure is defined for the whole treatment phase.
6. Number of flares in PV and in all participants: count number of flares as assessed by the investigator. A new flare only emerges after a new DC. Number of flares are counted over the whole treatment + follow-up phase, between first DC and CRmin (or end of treatment period for participants without CRmin) and after CRmin. The initial flare at baseline (if applicable) is not counted.

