Summary statistics on NCPD, cumulative prednisone dose, number of days and proportion of days with prednisone equivalent dose ≤ 10 mg will be provided for PV participants and an ANCOVA model with factors for treatment and the stratification variables will be applied on NCPD over the whole treatment phase only. Least square (LS) means and standard error (SE) with 95% 2-sided CI for placebo and efgartigimod will be reported, along with the difference in LS means of IMP vs placebo (with SE), 95% 2-sided CI, and 2-sided p-value. A non-parametric stratified Mann-Whitney test will be performed as sensitivity for PV participants. The 2-sided p-value resulting from this hypothesis test will signify whether the null hypothesis that the distributions of the NCPD for both treatment arms are identical can be rejected. The test will be conducted at a significance level of $\alpha=0.05$. A supplementary analysis using the treatment policy strategy applying the same ANOVA model will be done.

The table with summary statistics on NCPD will be repeated by subgroups, for PF participants and overall.

Time to CR and Time to DC will be descriptively presented with median times, quantiles and number and percentage of participants censored and with event. In addition, Kaplan-Meier survival plots by treatment arm will be produced (as in-text figures only). Both treatment groups will be compared using the stratified Fleming-Harrington weighted logrank statistic FH (1,0). Also the Cox proportional hazard model will be used: the model will include treatment as fixed effects and stratification factors as covariates. The HR for efgartigimod vs. placebo will be provided, along with the associated 95% 2-sided Wald-type CI and 2-sided p-value. The table will be produced for PV participants and overall. The descriptive statistics will also be presented by subgroups.

Duration of CRmin and other 'time to event' parameters of the 'other secondary endpoints' in section 4.1.2.3 will be descriptively presented and treatment groups will be compared using the logrank statistic.

	Statistical Analysis Plan	
ARGX-113-1904	Final analysis	Final 2.0 of 22NOV2023

Frequency tabulations will be provided for the percentages of treatment failure and its different reasons. Failure rates will be compared using the same CMH-test as for the primary endpoint analysis.

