9.2 SAS CODE

9.2.1 *MMRM model*

Calculate &meanbase. as mean of base of all unique participants in FAS.

[REDACTED]

9.2.2 *ANCOVA model*

[REDACTED]

Note: this is the script for NCPD. For other variables this code needs to be adapted according the model specifications in section 4.1. For example, for PDAI, the dependent variable is CHG and the baseline value needs to be added to the set of covariables.

9.2.3 *Time to event analysis: stratified Fleming-Harrington weighted logrank test*

[REDACTED]

9.2.4 *Time to event analysis: logrank test*

[REDACTED]

	Statistical Analysis Plan	
ARGX-113-1904	Final analysis	Final 2.0 of 22NOV2023

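### Time to CRmin is planned with a log-rank test that appears to be unstratified, and SAP 4.1.3/8.1 and SAP 6.1 do not agree on whether it gets a hazard ratio

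*SAP*

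**What the plan says.** SAP 4.1.2.3, item 2, defines the endpoint: "Time to CRmin in PV, PF and all participants: same derivation as third key secondary endpoint (composite strategy) but using date of achieving CRmin". The section is headed "OTHER SECONDARY ENDPOINTS (NOT ALPHA CONTROLLED"), and time to CRmin is not in the fixed sequence of SAP 4.1.4. SAP 6.1 lists it as an extra endpoint that the protocol does not contain. SAP 8.1 gives it three tables (14.2.1.3.1.1 to 14.2.1.3.1.3, for PV, PF and PV+PF). All three are marked topline and titled as descriptive statistics with a log-rank test.

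On the comparison, SAP 4.1.3 says that duration of CRmin and the other time-to-event parameters "in section 4.1.2.3 will be descriptively presented and treatment groups will be compared using the logrank statistic".

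Other endpoints are treated differently:
- Time to CR and time to DC (SAP 4.1.2.2): "Both time to event endpoints will be statistically evaluated using the stratified Fleming-Harrington weighted logrank statistic FH (1,0"). SAP 4.1.3 adds a Cox model with the stratification factors as covariates, reporting a hazard ratio and 95% CI. SAP 8.1 lists Cox tables for both endpoints.
- Primary endpoint (SAP 4.1.3): "A stratified CMH test will be calculated with the stratification factors of disease status, disease severity, and body weight at randomization".
- Design (SAP 1.2): "Randomization will be stratified by disease status (relapsing and newly diagnosed), disease severity" and body weight at 77.5 kg.

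The heading of SAP 9.2.3 includes the word stratified; SAP 9.2.4 is headed only "Time to event analysis: logrank test". The code under both is blacked out. SAP 6.1 also names a Cox model as an extra analysis for time-to-event endpoints, without saying which.

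**The concern.** Time to CRmin is the time-to-event counterpart of the primary endpoint and will be read beside it at topline. If its test is unstratified, it departs from the analysis of nearly every other efficacy endpoint, and no reason is given. After stratified randomisation, an unstratified log-rank test is conservative when the factors are prognostic, so it gives up some power.

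The second issue is what the reader gets besides a p-value. At the planning rates, medians and quantiles would say little, so a hazard ratio would be the natural summary of the effect on timing. The SAP leaves open whether one will be produced.

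**Working it through.** **1. Is the test stratified?** The relevant SAP text, side by side:

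| Endpoint | Comparison in SAP 4.1.3 | Factors named? |
|---|---|---|
| CRmin, DC, CR, treatment failure, flare (proportions) | CMH | yes |
| NCPD, number of flares, C-GTI, PDAI | ANCOVA | yes |
| ABQOL, EQ-5D-5L VAS | MMRM | yes |
| Time to CR, time to DC | stratified FH(1,0), Cox | yes |
| Time to CRmin, duration of CRmin | log-rank | no |

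The missing word and the 9.2.3/9.2.4 headings point the same way. Table titles do not settle it, because the CR and DC tables in SAP 8.1 are also titled as log-rank tests.

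**2. Is a hazard ratio planned?** By SAP 4.1.3 and 8.1, no. By SAP 6.1, possibly. A missing table is not conclusive: SAP 4.1.3 analyses time to first flare like time to CR or DC apart from the test statistic, which would include Cox, yet SAP 8.1 lists no Cox table for flare.

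**3. Do the factors bear on CRmin timing?** Protocol 4.2 says the time of CRmin depends on body weight. Protocol Table 3 has one extra 2-week step from 77.5 kg, which is also the stratification cut-point. Counting weeks from CR to CRmin for a participant who reaches CR at 0.5 mg/kg:
- below 77.5 kg: 2 (hold) + 2 (20 mg) + 3 (17.5, 15, 12.5 mg) + 8 (10 mg) = 15
- from 77.5 kg: 2 + 2 + 2 + 3 + 8 = 17

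The documents give no effect sizes for disease status or severity.

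**4. The plan's own figures.** The SAP gives no power figure for time to CRmin. The figures in Protocol 9.3 reproduce. For 50% vs 20% at 2:1, exact power of Fisher's test is 89.7% with 41 on placebo and 90.6% with 42, so 42 is the smallest number above 90%. For 34% vs 11% with 61:122 (183 PV), the pooled normal approximation gives 94.7%, against the stated 95%.

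**5. What would stratifying change?** Two simulations compared the unstratified and the 8-cell log-rank test, with 183 PV participants, 2:1 blocks within cells, and events counted to week 31. The stratum effects are assumptions.

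Simulation A: exponential time to CR plus the 15- or 17-week lag, CRmin 40% vs 20%, 6,000 runs. The Monte Carlo SE is about √(0.8×0.2/6000) = 0.5 points.

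| Assumed stratum effects | Unstratified | Stratified | Difference |
|---|---|---|---|
| Weight lag only | 79.0% | 78.6% | −0.4 |
| Severe HR 0.5, relapsing HR 0.75 | 79.7% | 81.3% | +1.6 |
| Severe HR 0.33, relapsing HR 0.6 | 80.4% | 83.7% | +3.3 |

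In the last row, rejection under the null is 4.3% unstratified and 5.2% stratified. At 50% vs 20% all powers exceed 98%.

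Simulation B: three 50/50 factors, each with log hazard ratio b (b = 0.5 is HR 1.65, b = 1 is HR 2.72); CRmin possible from week 15; 0 or 2 weeks' delay for heavier participants; 800 runs. The SE is about √(0.55×0.45/800) = 1.8 points for power near 55%, and √(0.05×0.95/800) = 0.8 points under the null.

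| CRmin rates | b | Unstratified | Stratified |
|---|---|---|---|
| 30% vs 30% (null) | 0 | 4.3–4.6% | 4.0–5.4% |
| | 0.5 | 3.0–4.4% | 4.0–4.9% |
| | 1 | 2.9–3.1% | 4.8–5.3% |
| 35% vs 20% | 0 | 54–55% | 53–55% |
| | 0.5 | about 56% | about 58% |
| | 1 | 57–58% | 66–68% |
| 34% vs 11% | 0 and 0.5 | 94–96% | 94–96% |
| | 1 | about 96% | 97–98% |
| 50% vs 20% | any | at least 98% | at least 98% |

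**6. What would the descriptive summary show?** With 20% of placebo participants reaching CRmin, neither the placebo median nor the 25% quantile would be reached unless early censoring is heavy. With 50% on efgartigimod, the median would be reached only near the end of the period.

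**The case against.** The strongest reply is that this is a supportive endpoint with little to gain. It lies outside the alpha-controlled sequence, so no confirmatory claim rests on it. The unstratified test is valid and errs on the conservative side, so it cannot produce an excess of false positives. The only stratum effect that comes from the documents, the weight lag, brings no gain. The larger gains need assumed prognostic effects and, for 8 to 11 points, a 35% response that lies below the 40–50% range in Protocol Table 6. The effect on CRmin is already estimated by the adjusted difference, the odds ratio and the week-30 landmark analysis. All of this stands, and it keeps the point minor. It does not remove the inconsistency in the text, and none of those estimates describes timing.

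Two stronger readings are tempting, and the documents support neither:
- A reader might infer that the SAP certainly ignores the factors. That rests on a missing word and two headings, with the code blacked out and the term log-rank used loosely in table titles.
- A reader might infer that no effect estimate is planned at all. SAP 6.1 names Cox models for time-to-event endpoints without limiting them to CR and DC, so the finding is a disagreement between sections.

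The match between randomisation and strata is also incomplete. SAP 4.1.3 says Japanese and PF participants were randomised without these factors, and the analysis takes eCRF values. On the targets in Protocol 1.1 that is 9 of 183 PV participants (4.9%), and 9 + 30 = 39 of 213 overall (18.3%). For them, stratifying is covariate adjustment rather than a reflection of the randomisation.

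**Conclusion.** The point holds as a minor one. As written, time to CRmin is most naturally read as having an unstratified log-rank test, and the SAP sections disagree on a hazard ratio. The test would be valid but conservative if the factors are prognostic. The gain from stratifying is about 0 to 3 points of power at 40% vs 20% under the stratum effects assumed in simulation A. It reaches 8 to 11 points only at 35% vs 20% with each factor at HR 2.72, and it is negligible at 50% vs 20%. These sizes rest on assumed prognostic strengths, equal or 50/50 cells, and all participants being randomised within the cells.

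**What to change.** - In SAP 4.1.3 and 9.2.4, state that the log-rank test for time to CRmin is stratified by disease status, disease severity and body weight (eCRF values) for PV and PV+PF. For PF, use disease status only, in line with the existing rule for stratified PF analyses.
- In SAP 4.1.3, add a Cox hazard ratio with 95% CI for time to CRmin in PV and PV+PF, built as for CR and DC, and add the two tables to SAP 8.1.
- In SAP 6.1, name the endpoints to which the Cox model applies, so that it agrees with 4.1.3 and 8.1.
- Optional: report Kaplan-Meier CRmin probabilities at fixed weeks. These are not currently planned for CR or DC either.

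The cost is some SAP text and programming, with no new data. If the factors are not prognostic, the loss of power is negligible: the 0.4 points seen in simulation A lie within its Monte Carlo error. Cells may be thin. At 34% vs 11%, about 48 events over 8 cells is 6 per cell on average, and a cell with only one arm represented adds nothing to the test.
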